### **Statistical Methods And Considerations**

For all sub-studies (1a, 1b, and 1c), data management and statistical analysis will be performed by the Krupp Biostatistical and Data Management Core and will employ the Krupp Data System (KDS). A computer-generated randomization list will be prepared by the study biostatistician and will be used to randomize subjects into one of the two treatment groups with equal probability. For sub-study 1c only, equal number of subjects based on age (18-55 and  $>55$ ) and BMI ( $<30$  and  $\geq 30$ ) will be randomized to the treatment groups. For all sub-studies, randomization tables will be prepared at the beginning of the study and will be maintained by the study biostatistician.

Within each of the sub-studies, the comparability of the two treatment groups in terms of baseline demographic and clinical features will be tested with analyses of variance (ANOVAs) for continuous variables and Chi-square analyses for dichotomous variables. Descriptive statistics and exploratory graphing will be used to assess the distribution, normality, and homogeneity of the data. If needed and applicable, the continuous outcome data will be transformed using an appropriate transformation such as a log transformation. Missing data will be examined to assess randomness and informativeness using methods developed by Diggle (1989). Similarly, we will test whether dropout is random or systematic by comparing the dropouts with the study completers in terms of the baseline data. An absence of significant differences would support the random nature of dropout.

The primary aims of our data analytic strategy will be directed toward assessing the safety of the interventions, antibody titers, vaccine side effects, adherence to treatment, and retention rate. This will help to provide guidance to inform any

required methodological modifications. The safety data will be summarized by treatment group and site. Adverse events will be tabulated. These will include the number of participants for whom the event occurred, the rate of occurrence, and the severity and relationship of adverse events to study treatment. Safety data will be analyzed using ANOVAs for continuous variables and Chi-square analyses for dichotomous variables at each time point. Wilcoxon-Mann-Whitney rank-sum test will be used to analyze treatment arm versus control arm across study visits and sites. We anticipate using non-parametric tests because the majority of the outcome measures used in our research may not be normally distributed. The Kruskal-Wallis test will be used to determine whether samples from each of the two arms originated from the same distribution. Since nonparametric tests are based on complete data and ignore missing follow-up data, general linear mixed regression modeling (Gibbons et al, 1988; Hedeker et al, 199; Laird et al, 1982) will be used to confirm the results of the nonparametric tests. The two arms will be compared over time with a focus on the treatment by Time interaction effect. Mixed regression modeling offers robust handling of missing data (Little, 1996) with an assumption that the data is missing at random. This method allows the inclusion of subjects with missing data or those who were terminated early in the study, without relying on data imputation procedures. This method provides an estimate of the individual variability around the population trend, the variability of the individual intercepts (baseline values) and slopes (changes across time), and the correlation between them. Co-variance structure will be chosen based on Akaike's Information Criterion (AIC). Random group level treatment effects will also be evaluated for importance based on the model AIC. Denominator degrees of freedom will be calculated using the Kenward-Roger small sample correction.

A detailed list of feasibility outcomes is provided in the previous section. Briefly, feasibility outcomes will be assessed by determining: 1) Numbers of potentially eligible and ineligible patients, number contacted, and consent rates. 2) Feasibility of recruiting sites in which staff are interested in participating in a future main trial. 3) Rate of retention in the trial, including response rates to questionnaires and individual measures. 4) Intervention fidelity and adherence using case report forms and patient-completed personal diaries. 5) Determining the primary outcome measure for the main trial by assessing and comparing sensitivity to change of the measures and other statistical properties, comparing follow-up rates of different methods of data capture and of individual measures, and evaluating which outcome measures best reflect the patients' recovery goals, as identified from the collected data.

As indicated above, the primary aims of our data analytic strategy for sub-studies 1a and 1b will be directed toward examining the safety and feasibility of the treatments. Although it is not our major focus, we also aim to estimate effect sizes to assist in future power calculations. However, recent work by Kraemer (2006) has highlighted important limitations of this aim due to the large standard error surrounding the pilot study effect size. As a result, the primary focus of our analyses will remain on safety and feasibility and we will report our findings with this limitation in mind. Our goal is to collect important data regarding our ability to implement recruitment strategies, and the safety and feasibility of the treatments and measurements. Information derived from this research will lead to better-designed full-scale studies and help inform decisions regarding whether it is worthwhile to commit additional resources to future treatment development. Due to our small sample size, our statistical analytical findings will be interpreted with caution. Sub-study 1c will include sufficient number of subjects to test for treatment efficacy.

Data will be analyzed from all randomized subjects. All statistical tests will be two-tailed. Differences will be considered statistically significant provided a p-value of 0.05 or less is obtained. The significance level for the tests will be adjusted with a Bonferroni correction for multiple comparisons, if needed. Data will be analyzed using SPSS version 27.

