#### **(2) End-of-Treatment:**

For patients who are not hospitalized, the study phlebotomist will collect their specimens at Day 14 for the following laboratory tests:

- Basic Metabolic Panel
- Complete Blood Count with Differential
- Liver Function Testing

- Prothrombin Time and Partial Thromboplastin Time
- Ferritin
- D-Dimer
- Lactate Dehydrogenase
- C-Reactive Protein
- Troponin
- T-cell differentiation panel
- Salivary or nasal swab samples will be collected for SARS CoV-2 viral load assays
- Plasma, serum, and whole blood will be collected and banked for cytokine, immunological, and metabolomic assays

For subjects who require hospitalization by Day 14, results of the following laboratory tests will be obtained from their hospital records (please note that these tests are routinely conducted as part of COVID-19 treatment and results should be available within subjects' medical records):

- Admission Basic Metabolic Panel,
- Complete Blood Count with Differential, and
- Liver Function Testing.

Please note that medical records will also be reviewed for SARS-CoV-2 viral load, any inflammatory biomarkers (CRP, procalcitonin, IL-6, ferritin, D-dimer, lactate dehydrogenase) as well as markers of myocarditis (troponin, CK-MB) and further lymphocyte differentiation (T-Cell differentiation panel).

Sub-study 1c:

Sample collection will occur at the following time points:

- Single dose vaccine (such as J&J): baseline, day 14, day 28, and 6 months post vaccination
- Two-dose vaccine (such as Pfizer or Moderna): baseline, day 14, two weeks after your second dose, and 6 months post vaccination
- Vaccine booster: baseline, day 3, day 14, and 6 months

For all time points:

The following test will be run to establish values of immunogenicity against SARS CoV-2:

- SARS CoV-2 IgG antibody titer
- Cytokines and T-cell assays

For time points Baseline and Day 14:

The following laboratory assays will be conducted to ascertain FoTv safety:

- Basic Metabolic Panel
- Liver Function Tests

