#### **Sub-study 1c:**

This sub-study will include 266 subjects as well as an additional 53 participants to account for an anticipated 20% rate of study dropout. Number of subjects was adjusted due to recent introduction of the vaccination booster shot and availability of extra funding which allows us to expend study aims to further test of the treatment efficacy.

For other objectives of sub-study 1c, sample size was determined using the RMASS program (<http://tigger.uic.edu/~hedecker/ml.html>)

Based on our sample size estimation, we are confident that the enrollment of 66 (1a/1b) or 266 (1c) participants will provide a sufficient number of subjects to evaluate these outcomes with medium effect size while also ascertaining safety (Tubert-Bitter et al., 2000; Zhang P, 2003).

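### Sub-study 1c pools three vaccine regimens on three sampling schedules without adjusting for regimen, and its lead rank tests ignore baseline IgG: a cheap gain in precision is left unused

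*Combined protocol and SAP*

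**What the plan says.** Section 10 admits to 1c any adult who is due to be vaccinated against COVID-19, subject to a short list of exclusions. Under Clinical Laboratory Measurements, IgG is measured at every sample, on one of three schedules. People having a booster give their second sample within days: "Vaccine booster: baseline, day 3, day 14, and 6 months". For people on a one-injection primary course, the line in the protocol is instead "Single dose vaccine (such as J&J): baseline, day 14, day 28, and 6 months post vaccination". The remaining group has its third sample tied to the later injection: "Two-dose vaccine (such as Pfizer or Moderna): baseline, day 14, two weeks after your second dose, and 6 months post vaccination".

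Under Statistical Methods And Considerations, the allocation rule reads "For sub-study 1c only, equal number of subjects based on age" and goes on to name two age groups and two BMI groups. Regimen is not an allocation factor. For the comparison of arms, the section says "Wilcoxon-Mann-Whitney rank-sum test will be used to analyze treatment arm versus control arm across study visits and sites" and adds a Kruskal-Wallis test. It then brings in a mixed model to confirm the rank tests: "Since nonparametric tests are based on complete data and ignore missing follow-up data". Of that model it says "The two arms will be compared over time with a focus on the treatment by Time interaction effect". The model has individual intercepts, described as baseline values, and individual slopes. No full model formula is given, and no regimen, regimen-by-visit, age or BMI term is named.

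Section 6 lists a higher peak antibody response and a slower post-peak decline among the primary objectives of 1c.

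**The concern.** Regimen is likely to be a strong source of variation in IgG, and the schedules do not line up. The second sample falls at day 14, day 14 or day 3. The third falls at day 28, two weeks after dose 2, or day 14. An analysis that pools regimens without a regimen term leaves those differences in the error. The rank tests also discard the baseline titre, which is already measured. The plan then puts the rank tests ahead of the mixed model, although it acknowledges that they drop incomplete follow-up.

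At stake is the chance of detecting a real effect on titre in the one sub-study that the plan says is large enough to test efficacy. A second, smaller matter is the decline objective. A treatment-by-time interaction over all visits mixes the rise after vaccination with the later fall.

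**Working it through.** **Inputs from the documents.** Two-sided alpha 0.05; 266 participants, 133 per arm; 20% dropout; a medium effect with no number attached. The figure of 266 cannot be reproduced, because power, numeric effect size, SD, correlation and number of visits are not stated.

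**Completers.** If 266 includes dropout (Research Design and Methods), 266 × 0.8 / 2 = 106.4 per arm. Sample Size Justification can also be read as 266 plus 53: "This sub-study will include 266 subjects as well as an additional 53 participants to account for an anticipated 20% rate of study dropout". Then 319 × 0.8 / 2 = 127.6 per arm. I use 106, 127 and 133.

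**Step 1: general gain.** Covariates explaining a share R² of outcome variance turn a standardised effect d into d / √(1 − R²). Noncentral-t power:

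| Starting point | R² 5% | 10% | 20% | 30% | 40% |
|---|---|---|---|---|---|
| 80% unadjusted (d = 0.387 / 0.353 / 0.345 at 106 / 127 / 133) | +2.0 | +4.0 | +7.9 | +11.8 | +15.1 points |
| d = 0.5, 106 per arm (95.2%) | +0.9 | +1.7 | +3.0 | +3.9 | +4.5 |
| d = 0.5, 127 per arm (97.8%) | +0.5 | +0.9 | +1.6 | +2.0 | +2.1 |
| d = 0.5, 133 per arm (98.2%) | +0.4 | +0.8 | +1.3 | +1.6 | +1.7 |

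**Step 2: how much variance regimen could carry.** Assume three equal regimens with means 0, g/2 and g, and within-regimen SD 0.5 log10. The between-regimen variance is g²/6. For g = 0.5 / 1.0 / 1.5 the share g²/6 ÷ (g²/6 + 0.25) is 14 / 40 / 60%. A 10:90 mix of two regimens gives 8 / 26 / 45%.

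**Step 3: the rank tests.** Simulation with 4,000 runs per cell, true effect 0.2 log10, age and BMI effects of 0.2 SD each, baseline correlation 0.5, 106 per arm:

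| Analysis, power % | g = 0 | 0.5 | 1.0 | 1.5 |
|---|---|---|---|---|
| Plain rank-sum | 80 | 74 | 57 | 41 |
| Van Elteren by regimen | 80 | 79 | 80 | 80 |
| Model: age, BMI, regimen | 83 | 82 | 83 | 82 |
| Model: regimen, baseline | 91 | 90 | 91 | 91 |
| Model: all four | 91 | 91 | 92 | 91 |

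At 127 per arm, rank-sum gives 87 / 81 / 66 / 46% and van Elteren 87 / 86 / 87 / 87%. Age and BMI add 0.1 to 0.7 points once regimen and baseline are in. If the baseline correlation is 0.2, the full model gives about 84 to 85% at 106 per arm (run at g = 0.5 and 1.0). With no true effect, rejection was 4.2 to 4.9%.

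**Step 4: the planned mixed model.** Take change from baseline as a two-visit stand-in for its treatment-by-time test, at 106 per arm. The SD of change is 0.5 × √(2(1 − ρ)), and a regimen gap that is equal at both visits cancels.

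- ρ = 0.5, equal gaps: SD 0.5, d = 0.4, power 83% at any g.
- ρ = 0.5, gap of 1.0 at follow-up only: variance 0.25 + 1/6 = 0.417, d = 0.31, power 61%.
- ρ = 0.2, equal gaps: SD 0.632, d = 0.316, power 63%.
- For comparison, adjusting for regimen and baseline leaves SD 0.5 × √(1 − ρ²): 0.433 (92%) at ρ = 0.5 and 0.490 (84%) at ρ = 0.2.

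**Step 5: decline.** Suppose the third sample is the peak and 6 months is 182 days. The peak-to-6-month interval is then 182 − 28 = 154 days for single-dose and 182 − 14 = 168 for booster. For two-dose it is 140 to 147 days if counted from dose 1 (assuming dose 2 at day 21 to 28), or 168 from dose 2. With intervals 154 / 168 / 147, decline slowed by 0.2 log10, and regimens differing in decline by 0 / 0.5 / 1.0 log10, a slope comparison without regimen has 82 / 75 / 59% power, and with regimen 82 / 81 / 83%.

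**The case against.** Four points on the other side carry weight.

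1. The mixed model already uses baseline through subject intercepts, which also absorb regimen differences that stay constant over visits. This stands. The drop to 41% belongs to the rank test and should not be attributed to the mixed model. Step 4 shows that the model still loses when regimens differ in their change over time, or when baseline predicts follow-up weakly.

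2. At d = 0.5 the trial has power to spare. This also stands, if that is what medium means. The documents do not say.

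3. The statistical text is a summary, and silence is not exclusion. The rank tests are anticipated rather than fixed, log transformation is allowed, and the rank-sum sentence follows the safety sentences. This is partly right. But antibody titres are listed among the primary analytic aims just before, no other titre analysis is given, and the text does not look tailored to 1c: it speaks of sites, whereas 1c is single-site.

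4. A reader might infer that the plan has no analysis of decline, or that it would judge decline by comparing levels at 6 months. Neither is supported. Treatment-by-time with individual slopes is planned, and no section makes a 6-month level comparison the decline analysis. What remains is narrower: the interaction is not confined to the post-peak period.

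**Conclusion.** The point holds as an inexpensive improvement in precision. A reader might go further and infer that leaving out regimen, or the age and BMI allocation groups, biases the comparison or inflates type I error. It does not: randomisation protects the unadjusted comparison, and simulated rejection under no effect stayed between 4.2 and 4.9%. That assurance covers a pre-specified outcome only.

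The benefit ranges from under 1 point (d = 0.5 with weak covariates) to about 15 points (80% starting power with 40% of variance explained). It is larger for the plain rank-sum test only if regimens differ by about 1 log10 or more. Regimen and baseline titre supply nearly all of it; age and BMI matter little, assuming effects near 0.2 SD each. Every regimen gap, mix, SD and correlation used here is an assumption. Confidence in the omission is high; confidence in its size is medium at best.

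**What to change.** Amend the SAP text for 1c as follows.

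- **Deciding analysis.** Make a mixed model of post-baseline log IgG the deciding antibody analysis: arm, visit, arm-by-visit, log baseline IgG, regimen, regimen-by-visit, age group and BMI group.
- **Visits by role.** Define visits within each regimen as early sample, designated peak sample and 6 months, not by sample order, so that arm-by-visit has one meaning. Choose the peak sample from the existing schedule before unblinding. The peak contrast is the arm difference at that visit.
- **Decline.** Narrow the existing treatment-by-time analysis to the arm difference in log-titre slope from the designated peak sample to 6 months, with time in actual days and regimen-specific slopes. State which dose the 6 months count from in two-dose participants.
- **Rank test.** If one is kept, use van Elteren stratified by regimen, as support only. Do not add the four age and BMI cells as strata: the resulting 12 strata cost a further 1.4 to 2.6 points.

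No new data are needed. Regimen must be known to schedule the samples, age and BMI are needed for allocation, and baseline IgG is already drawn. The model spends a few degrees of freedom. If regimens turn out not to differ, the stratified rank test gives up 0.5 to 0.8 points of power against the plain one.

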#### B. Feasibility:

The following feasibility data will be collected and assessed :

- 1) Recruitment:
  - a. Recruitment sites (number, location, and method of their selection)
  - b. Factors influencing recruitment rate
  - c. Methods used for subject recruitment
  - d. Number of subjects:
    - I.
      - i. Initially contacted
      - ii. Initial interviewed
      - iii. Consented
      - iv. Baseline data collected
  - e. Reasons for non-participation:
    - i. After initial contact and/or initial interview
    - ii. After consent process
    - iii. After initial data collection or throughout the study
    - iv. Until end of study
  - f. Reasons for participating in and completing study

2) Randomization:

- a. Testing effect of randomization process on distribution of demographic, co-morbidity, and other background characteristics
- f. Testing randomization process on their baseline main outcomes
- g. Examining acceptability of the randomization process and its effect

3) Missing data:

- a. Differences in rates of missing data between medication and placebo groups and per time point
- b. Pattern of missing data

4) Retention rate:

- a. Differences in retention between medication and placebo groups
- b. Factors influencing these differences

5) Subjects' satisfaction with:

- a. Study procedures
- b. Study implementation and staffing
- c. Medication delivery methods
- d. Data collection timepoints and outcomes

6) Medication fidelity with:

- a. Delivery methods
- b. Number of successful and failed deliveries
- c. Assessment methods
- d. Timing and method of feedback

7) Study improvement procedures/maintaining documentation of:

- a. Study/protocol development, revision, and modification
- b. Issues and concerns with implementing recruitment strategies
- c. Issues and concerns with accessing, distributing, and tracking of medication and placebo
- d. Issues and concerns with measurements:
  - i. Number of measurements
  - ii. Time requirements of measurements
  - iii. Redundancy among measurements
  - iv. Positive or negative carryover

Sub-study 1c: FoTv vs placebo for use as an adjunct to COVID-19 vaccination.

The primary objectives of this study are to determine whether FoTv, when taken for four consecutive days starting the day of COVID-19 vaccination, is safe and associated with:

- An enhanced peak COVID-19 antibody response
- A reduced rate of post-peak antibody decline
- Reduction in side effects from COVID-19 vaccination

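### Fix the scale of the sub-study 1c IgG titre in advance: a scale chosen after looking at the data can decide the sign of the antibody-decline result

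*Combined protocol and SAP*

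**What the plan says.** Section 6 (Specific Aims, Sub-study 1c) lists among the primary objectives "An enhanced peak COVID-19 antibody response" and "A reduced rate of post-peak antibody decline". Neither has a scale, a formula or named visits.

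Section 9 (Clinical Laboratory Measurements, Sub-study 1c) measures the "SARS CoV-2 IgG antibody titer" at every time point, on schedules that differ by vaccine. Two examples are "Single dose vaccine (such as J&J): baseline, day 14, day 28, and 6 months post vaccination" and "Vaccine booster: baseline, day 3, day 14, and 6 months".

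Section 9 (Statistical Methods and Considerations) governs the scale. It first says: "Descriptive statistics and exploratory graphing will be used to assess the distribution, normality, and homogeneity of the data". It then says: "If needed and applicable, the continuous outcome data will be transformed using an appropriate transformation such as a log transformation". No outcome, criterion or timing is named, and the plan does not say whether the check is made blind to treatment. The same section continues: "We anticipate using non-parametric tests because the majority of the outcome measures used in our research may not be normally distributed". A linear mixed model, focused on the treatment-by-time interaction, is to confirm the rank tests. Log titre, geometric mean titre, fold change and half-life of antibody are mentioned nowhere.

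**The concern.** For a titre, the scale is more than a question of normality, because it defines what decline means. On the raw scale decline is units lost; on the log scale it is the proportion lost. If FoTv raises the peak by a ratio and both arms then lose the same proportion, the FoTv arm loses more units, and a raw analysis of change reads this as faster decline. Success on the first primary objective would then look like harm on the second.

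The plan leaves both routes open. Non-normal titres could lead to the log, or to rank tests with no transformation at all. Since the choice follows sight of the data, the direction of a primary result could turn on it.

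**Working it through.** The plan gives no figure on this point, so there is none to reproduce.

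**Inputs from the documents.** There are 133 per arm (Section 9) and 20% anticipated dropout (Sample Size Justification), so 133 × 0.8 = 106 evaluable per arm. Tests are two-sided at 0.05.

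**Assumed inputs.** The documents give no titre SD, peak ratio or rate of decay, so ranges are used.

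**Step 1: algebra.** Let P be the peak and f the fraction remaining at 6 months. Raw loss is P × (1 − f). With the same f in both arms, the ratio of raw losses equals the ratio of peaks. For example, 1000 falling to 200 and 1500 falling to 300 are both 80% falls, but the raw losses are 800 and 1200, a ratio of 1.5. On the log scale both changes are log10(0.2) = −0.70. This step needs no SD.

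**Step 2: how much slower must true decay be to hide the effect?** Take a control half-life of 76 days, from day 28 to day 180 (152 days): f = 2^(−152/76) = 0.25. With a peak ratio of 1.5, equal raw loss needs 1.5 × (1 − f′) = 0.75, so f′ = 0.5, a half-life of 152 days. The FoTv half-life would have to double merely to show equal raw decline. Over control half-lives of 50 to 110 days the factor runs from 2.4 down to 1.8.

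**Step 3: simulation with identical proportional decay.** Peak log10 titre is Normal(3, s) with s = 0.3 to 0.5, and the FoTv arm is shifted by log10 of the peak ratio. Log10 change is Normal(−0.7, 0.25) in both arms, with 106 per arm and 1,500 runs per setting. Share of trials declaring significantly faster decline with FoTv:

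| Peak ratio | t-test, raw change | Rank test, raw change | t-test, log10 change |
|---|---|---|---|
| 1.5 | 47–96% | 68–98% | 2–3% |
| 1.3 | 23–66% | 37–72% | about 2% |

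The larger SD gives the lower figure. Repeat runs move single entries by up to about five points. The nominal rate in one direction is 2.5%.

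**Step 4: a second set of assumptions.** Take a half-life of 76 days in both arms, a peak ratio of 1.5, and natural-log SDs of 0.5, 0.8 and 1.0. Raw change is declared faster on FoTv in 100%, 87% and 64% of trials by t-test and 100%, 95% and 81% by rank test, against about 2.5% on the log scale. If FoTv truly lengthens the half-life by 25% (76 to 95 days, with an assumed SD of log decay of 0.3), the raw t-test still declares faster decline in 96%, 59% and 38% of trials and slower decline in almost none. The log analysis finds the benefit in about 100%.

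**Step 5: which planned tests depend on scale?** A rank test of titre at one visit gives the same result raw or logged. It can address the peak, and the level at 6 months, but not the decline. In the Step 3 setting with a ratio of 1.5, a rank test of the 6-month level favours FoTv in about 60–90% of trials. Decline needs either a change score or a treatment-by-time term, and both depend on scale.

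**Step 6: would the plan's check trigger the log?** The plan names no test. With Shapiro-Wilk as an illustration, normality of raw peak and raw change was rejected in both arms in 100% of the Step 3 trials (600 runs per setting). The check would flag such data. What the plan does next, log or rank test, is not settled.

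**The case against.** The strongest reply is that titres are skewed, the planned check would show it, and the log is the one transformation the plan names. Step 6 supports this. A reader might infer from the table that the plan as written has a false-result rate of 47–96%. The documents do not support that: the figures apply only if raw change, or a raw treatment-by-time term, is what gets analysed.

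A reader might also infer that the rank tests in general are compromised. They are not. The plan applies them across study visits and nowhere mentions ranks of change scores, and per-visit comparisons are unaffected by a log. For the same reason there is no case here that the anticipated rank analysis of the peak loses power by staying on the raw scale.

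Finally, the conflict assumes roughly proportional decay, which the documents do not state. If antibody fell by a constant absolute amount, the log scale would make a higher peak look like slower decline.

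All of this limits the claim. What stands is that nothing requires the log, that rank tests are offered as another answer to non-normality, and that the decline objective cannot be tested without a choice of scale. The doubt about the form of decay is itself a reason to state in advance whether decline means absolute or proportional loss.

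**Conclusion.** The point holds in conditional form. It is tempting to say that the two primary antibody objectives work against each other, but the plan does not commit to raw titres, so that goes too far. They conflict only if decay is roughly proportional and decline is analysed on raw change or a raw treatment-by-time term. In that case the direction of the decline result is wrong in a large share of trials under every non-null peak ratio examined, and a real slowing of decline can be reported as an acceleration. The sizes rest on assumed SDs, peak ratios and half-lives; the direction rests on algebra.

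The defect is that a choice made after seeing the data can decide the sign of a primary result. It should be corrected, since Section 9 presents 1c as large enough to test efficacy.

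**What to change.** Before unblinding, replace the conditional rule for IgG with the following:

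- All SARS-CoV-2 IgG analyses use log10 titre, whatever the normality checks show.
- The peak is reported as a geometric mean ratio at one named post-vaccination visit for each vaccine schedule in Section 9 (single-dose, two-dose, booster).
- Decline is defined as proportional: the between-arm difference in log10 change from that named visit to 6 months.
- Decline is estimated as a post-peak contrast in the mixed model. A treatment-by-time term over all visits would mix the rise with the fall, even on the log scale.

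The conditional rule can stay for other continuous outcomes. With the log scale fixed, equal half-lives give a significant decline difference in about 4–6% of simulated trials, both directions together, whatever the peak ratio. The cost is a few sentences in the statistical section, with no extra visits, samples or participants.
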